#### 10.8 Administration of investigational device

Only trained research staff will operate the device. TAN treatment is started by attaching an electrode clip to the tragus of each ear and switching the stimulation 'ON' by turning the dial from the off position (marked as 0 on the dial) to position 4 or 5 on the dial. Once the patient experiences a tingling sensation, the signal amplitude is reduced by turning the dial anti-clockwise for 1 division below the tingling sensation threshold. The device will then continue to apply the stimulation for a fixed duration. The electrode must remain attached to the tragus of the ear for the entire treatment session. At the end of the stimulation period, the device will automatically stop the treatment session. The jack-plug of each electrode is inserted into the socket of the device control unit and clipped onto the tragus. It is important that both electrodes are connected, one for each ear.

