#### 5.0 Participant eligibility criteria

#### 5.1 Inclusion criteria

- Age 18 years and over
- Requiring mechanical thrombectomy for acute ischaemic stroke under general anaesthesia and/or sedation
- Established hypertensive and/or hypertensive on admission for mechanical thrombectomy (systolic BP >140mmHg; diastolic BP >80mmHg)

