#### 6.4 Blinding

This is a triple-blind trial, with trial participants, care providers and endpoint assessors to the treatment group allocation. The primary outcome will be analysed by individuals masked to the patient treatment allocation and clinical outcomes. Afferent Medical Solutions Ltd will be unblinded to facilitate reporting of Serious Adverse Device Events (SADE) or Unexpected Serious Adverse Device Events (USADEs) to the MHRA. The blinded interventions are highly comparable, as the same device will be used for all participants randomized to either active stimulation or turned off. Final unblinding of all study participants will occur after the data set is locked.

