#### 6.7 Trial intervention

Each participant will have the Affex-CT device connected to both ears via electrical leads. The device will be preset to deliver either transcutaneous autonomic neuromodulation or no stimulation. In the treatment arm, the device will be turned 'On' by a trained member of the research team and the transcutaneous autonomic neuromodulation will be applied continuously until the end of the stimulation period when the device will be turned 'Off'. For the control arm, no stimulation will be applied.

The intervention will be administered across two time points in each participant. The first will be delivered for the entire duration of the mechanical thrombectomy procedure. The start of mechanical thrombectomy is defined at induction of anaesthesia which is the patient's arrival in the anaesthetic room but before being wheeled into the radiology suite. The end of mechanical thrombectomy is defined as the point the patient leaves the radiology suite to be taken to the post recovery anaesthetic room. The second will be delivered on the morning after mechanical thrombectomy regardless of the time when the first procedure was administered. This will happen typically in the morning between 0800-1200h for one hour (± 10 minutes). The duration of participation is seven days from the start of the mechanical thrombectomy procedure for each participant. No special dietary or 'life-style' requirements will be imposed (this study will gather efficacy data for the intervention while establishing the feasibility of a full-scale trial).

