# NIH Stroke Scale (NIHSS) measured before the start of mechanical thrombectomy and 24 hours after the procedure.

NIHSS will be assessed at the following time points by a member of the research team:

- any time point after admission to hospital but before induction of anaesthesia
- 24 hours from start of mechanical thrombectomy

Clinically recorded arrhythmias within the first 24 hours after the start of mechanical thrombectomy Defined as electrocardiograph evidence for cardiac rhythm as determined by the treating clinician either documented in the medical records and/ or recorded by a 12 lead ECG.

Absolute levels of serum high-sensitivity troponin-T levels measured before the start of the first transcutaneous autonomic neuromodulation and at the end of the second transcutaneous autonomic neuromodulation.

Additional blood samples to routine care will be collected to measure serum high sensitivity troponin-T (Elecsys, Roche Diagnostics) levels. Blood samples will be collected at any time after hospital admission but before the induction of anaesthesia and within two hours upon the completion of the second transcutaneous autonomic neuromodulation. The time of completion for transcutaneous autonomic neuromodulation is defined as when the device is switched 'on' and 'off' by a member of the research team. If blood samples are not collected, a protocol deviation will be recorded and data point classified as 'missing'.

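### Setting intensity by felt tingling cannot be done as written under general anaesthesia, and in patients able to report sensation it cues operator and patient to the arm, so the stated blinding is not secured

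*Protocol*

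**What the plan says.** **How intensity is set.** Protocol 10.8: "Only trained research staff will operate the device". They turn the dial up, and then: "Once the patient experiences a tingling sensation, the signal amplitude is reduced". Stimulation continues one step below the level that was felt. Section 10.12 lists tingling among the expected effects of the device.

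**What sham is.** Protocol 6.7: "For the control arm, no stimulation will be applied". Section 6.4 describes participants as "randomized to either active stimulation or turned off". Sections 6.1 and 6.7 also say that the device is preset to its arm.

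**State of the patient.** The inclusion criterion in 5.1 reads: "Requiring mechanical thrombectomy for acute ischaemic stroke under general anaesthesia and/or sedation". Under 6.7, session 1 covers the whole procedure, which is counted from induction. Session 2 lasts about an hour the next morning, between 08:00 and 12:00 (6.7, 10.10).

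**What is claimed.** Section 2.5 calls the trial triple-blind. Section 6.4 says that participants, those giving care and those assessing endpoints are blinded, and adds: "The blinded interventions are highly comparable, as the same device will be used for all participants".

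**Who scores NIHSS.** Appendix A: "NIHSS will be assessed at the following time points by a member of the research team". One time point is before induction and the other is 24 h from the start of thrombectomy.

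**The concern.** The titration step needs something that one group of patients cannot give and one arm cannot generate. That causes two separate problems.

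The first is feasibility. Under general anaesthesia the instruction has no input, and the protocol gives no alternative. How the level is set in session 1 is then left to whoever is at the bedside.

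The second is masking. In a patient who can describe sensation, a dial turned up with tingling points to active and a dial turned up without it points to sham. The person who learns this belongs to the team that scores NIHSS, a clinician-rated scale open to expectation. If operator and assessor are the same person, the 24 h score can be influenced by a belief about the arm, and the report would still call the trial triple-blind. This is a pilot for a larger trial (13.1), so an unexamined weakness in the sham would be carried forward.

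**Working it through.** The plan gives no figure on this point, so there is none to reproduce. The check sets the passages side by side and then bounds when the cue can act.

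**Step 1. Session 1 under general anaesthesia.** Section 10.8 speaks of what the patient experiences. The operator can learn this only if the patient communicates it, and an anaesthetised patient cannot. The step fails equally in both arms, so it does not separate them. The preset wording in 6.1 and 6.7 does not settle the matter, because 10.8 still has the operator adjust the dial to sensation. Section 6.1 places the device before the sterile field is prepared, but the order of titration and induction is not stated.

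**Step 2. Patients able to report.** These are patients awake at session 2 and patients responsive under sedation in session 1. If titration is done before induction, conscious patients in session 1 join them. Active can yield a threshold; sham cannot. Section 6.7 describes switching on only for the treatment arm and does not say what the operator does with a sham device. Section 10.11 allows current to be reduced at the participant's request for ear discomfort, which is a possible second cue. The documents describe no mock titration, no separation of operator from assessor, and no check of the blind.

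**Step 3. Does the cue come before the 24 h NIHSS?** Let *t* be the clock time at which thrombectomy starts and *s* the clock time at which session 2 starts the next day (08:00 to 12:00). The 24 h NIHSS is due at clock time *t* the next day.

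Hours from cue to NIHSS = max(0, *t* − *s*). The same number is the part of the 24 h primary window that remains after the session 2 cue.

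| Thrombectomy start | Session 2 at 08:00 | Session 2 at 12:00 |
|---|---|---|
| 08:00 or earlier | 0 h | 0 h |
| 10:00 | 2 h | 0 h |
| 12:00 | 4 h | 0 h |
| 14:00 | 6 h | 2 h |
| 18:00 | 10 h | 6 h |
| 22:00 | 14 h | 10 h |
| just before midnight | about 16 h | about 12 h |

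For starts up to 08:00, NIHSS falls due no later than session 2 begins. For starts between 08:00 and 12:00, the order depends on the session time. After 12:00, the session always begins first. For an 18:00 start, 6 to 10 of the 24 primary hours (6/24 = 25% to 10/24 = 42%) follow the cue. Where the cue arises in session 1 (Step 2), it can act on the whole window.

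**Step 4. Which outcomes are reached?**
- *24 h NIHSS:* directly, if the operator scores it. Protocol 6.1 puts device use and NIHSS in the same visit (Visit 3).
- *Arrhythmias:* Appendix A leaves these to the treating clinician, from the records or a 12-lead ECG. The operator's knowledge would have to spread.
- *Primary endpoint:* systolic pressures recorded in usual care and taken from the electronic record (6.1, Appendix A), analysed by masked individuals (6.4). It is reached only if knowledge of the arm gets to those managing blood pressure.

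**The case against.** The best defence has four parts.

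1. **The final level is set below sensation.** Tingling is meant to be brief. That helps masking during the session, but the titration itself has already supplied the cue.
2. **Other safeguards exist.** Boxes are unmarked (6.3), the primary analysis is masked (6.4), and blood pressure comes from routine records. These stand, and they largely protect the primary endpoint.
3. **NIHSS is a modest target.** Appendix A does not say that the operator scores it, and 6.4 says that assessors are blinded. Protocol 14.4 lists NIHSS among outcomes reported without testing, and SAP Table 6 has no p-value column. However, the SAP's general principles promise a treatment effect and p-value for every secondary outcome. Separation of the two roles is left unstated, and that is the gap.
4. **Details may be elsewhere.** The instructions for use are in the Investigator Brochure, and operators are trained by the manufacturer (10.7). Sham handling may be covered there. Even so, the protocol's own sections need to agree.

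Stronger readings are tempting, but the documents do not support them. A reader might infer that session 1 reveals the arm. Under general anaesthesia neither arm reports tingling, so this cue separates nobody. A reader might also infer that all 36 participants are affected. Protocol 4.0 says that many patients are neurologically impaired, sedated or delirious, and the SAP's sensitivity analysis expects some to leave before the repeat session.

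**Conclusion.** The point holds in a limited form. Section 10.8 cannot be carried out as written in session 1 under general anaesthesia. In patients able to report sensation, the blinding of participants and research staff stated in 2.5 and 6.4 is not secured as written.

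It would go too far to say that triple blinding is not delivered or that the primary result is biased. The cue reaches the operator and the patient; masked analysis and routine blood pressure recording are not directly broken. The main exposure is one secondary endpoint, the 24 h NIHSS, in patients whose session 2 begins before that assessment.

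The number affected cannot be given. The documents do not report thrombectomy start times, the split between general anaesthesia and sedation, how many patients can communicate at session 2, or how many leave before it. The timing bounds assume that session 2 falls on the next calendar day in the stated window and that NIHSS is done at 24 h from the start of thrombectomy. The conclusion also assumes that the Investigator Brochure, which was not available, does not already prescribe matched handling.

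**What to change.** 1. **Reconcile 5.1, 6.1, 6.4, 6.7 and 10.8** on how the device is handled in anaesthetised patients and in the sham arm, including the order of titration and induction. No setting or rule is proposed here.
2. **Make the blinding statement true.** Either describe identical handling in both arms that preserves the blind, or state in 2.5 and 6.4 that device operators, and patients able to report sensation, cannot be assumed blinded.
3. **Separate the roles.** In Appendix A, require that the 24 h NIHSS is scored by an existing team member who did not operate the device for that patient.
4. **Optional.** Record the operator's and the patient's guess of allocation after session 2 and report it by arm. This is useful for planning the larger trial but does not itself correct the text.

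The cost is some wording, a small constraint on the staff rota and, if item 4 is taken up, two CRF fields. The triple-blind label may have to be weakened. Sample size and the primary analysis do not change.

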# 4.0 Informed consent procedures

Patients presenting with acute ischaemic stroke are frequently unable to consent for themselves due to neurological impairment, sedation or delirium. For every 30-minute delay, the odds of achieving a good outcome are reduced by 50% from initial confirmation of stroke to thrombectomy achieving reperfusion. (PMID: 26956258) Therefore, due to the emergency clinical situation, VANS will adopt a research without prior consent (also referred to as deferred consent) where eligible patients will be enrolled in the study through consent from a Professional consultee who would be the named interventional radiology consultant in charge of the patient's thrombectomy care. The consultant will be asked to sign the Consultee Declaration Form. The consultant retains one copy of the form; one copy goes in the participant's medical notes and the third in the investigator site file.

The Principal Investigator retains overall responsibility for the informed consent of participants at their site and must ensure that any person delegated responsibility to participate in the informed consent process is authorised, trained and competent to participate according to the protocol and standards set by GCP. Delegation can only be to medically qualified research team members.

Following participant enrolment, a delegated member of the site research team will approach the patient's Personal consultee if available. This may be a family member, partner or friend. This Personal consultee will be fully informed about the trial by a member of the research team or the responsible clinician. Personal Consultees will be given a copy of the Personal Consultee Information Sheet. They will be asked to provide their opinion as to whether the patient would object in taking part in medical research. If they decide that the patient would not object they will be asked to sign the appropriate informed consent form. Two copies of this form will be made — one copy in the medical records, original in the investigator site file and one left with the representative.

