# **Waveform parameters:**

- Channel: Dual, isolated between channels
- Mode of operation: continuous,
- Pulse intensity: recommended range for the investigation is 0.1-8mA (device range is 0-80mA)
- Pulse Rate: 30 Hz
- Pulse width: 200 μsec
- Duration /Time: Continuous for 30min
- Wave Form: Bi-Phasic Asymmetrical square pulse
- Electrical specification:
- Battery 9v (6F22)
- Mechanical specification:
- Dimensions: 95(H) x 60(W) x 23(T) mm

NHS Trust

Weight: 115 grams (inc. battery)

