# 10.10 Usage schedules

- First administration will be for duration of mechanical thrombectomy [which typically lasts two hours]
- Second administration will be the morning after the mechanical thrombectomy [0800-1200h] which typically lasts one hour.
- No changes to usage schedule are required for different age groups or demographics.

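### Session 1 amplitude depends on a tingling report that anaesthetised patients cannot give, the stated 30-minute duration conflicts with the schedule, and the setting used is not a listed data item

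*Protocol*

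**What the plan says.** **Amplitude.** Protocol 10.8 is the only place in either document that says how the amplitude is set. The operator turns the dial to 4 or 5. "Once the patient experiences a tingling sensation, the signal amplitude is reduced by turning the dial anti-clockwise for 1 division" below the threshold. The rule does not distinguish the two sessions. Elsewhere there are only ranges: usually 1-4 mA (9.1), and 0.1-8 mA recommended on a device that can reach 80 mA (9.2). Section 10.11 allows the current to be lowered when the participant asks. The presetting in 6.1 and 6.7 concerns active or sham mode, not amplitude.

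**Patients and timing.** The inclusion criterion is "Requiring mechanical thrombectomy for acute ischaemic stroke under general anaesthesia and/or sedation". On session 1, section 6.7 says: "The first will be delivered for the entire duration of the mechanical thrombectomy procedure". It defines the start of the procedure at induction, on arrival in the anaesthetic room. Section 4.0 adds: "Patients presenting with acute ischaemic stroke are frequently unable to consent for themselves due to neurological impairment, sedation or delirium". On session 2, section 10.10 says: "Second administration will be the morning after the mechanical thrombectomy [0800-1200h] which typically lasts one hour".

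**Duration.** Section 9.2 says the device has been set to a list of parameters that includes "Duration /Time: Continuous for 30min". Section 10.8 says: "At the end of the stimulation period, the device will automatically stop the treatment session". Section 6.7 instead has staff switch the device off at the end of the procedure, and Appendix A says completion of stimulation "is defined as when the device is switched 'on' and 'off' by a member of the research team". Section 9.1 mentions at least 60 minutes daily.

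**Recording.** The lists in 6.6 collect start and end times of stimulation for both sessions. SAP Table 3 counts deviations. Neither includes the dial setting or current.

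**The concern.** The amplitude rule needs a patient who can say when tingling starts. For most of the planned stimulation time the patient is anaesthetised or sedated, and many will be neurologically impaired before that. No default is given for a patient who cannot answer, so the step meant to bring the current below sensory threshold cannot be carried out as written. The stated durations also disagree, so it is uncertain how long the device runs.

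At stake is what the active arm receives. Section 13.1 describes a pilot meant to supply data for a larger efficacy trial. If neither setting nor delivered minutes is known, a positive result gives no dose to carry forward. A null result could not be read against the dose actually given.

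**Working it through.** The planned sample size is not at issue and reproduces. The difference in SAP section 3 is 15 - 10 = 5 with SD 4. Diluted by 5% non-compliance in each arm it is 5 x (1 - 0.05 - 0.05) = 4.5. A two-sided 5% t-test with 90% power then needs 17.6, so 18 per arm and 36 in total.

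**1. Can the amplitude rule be carried out in session 1?**
- Under general anaesthesia: no report is possible, so the reduction is never triggered.
- Under sedation only, or in the moments before induction: a report is possible in some patients. No section schedules titration there, and 4.0 says impairment is frequent.
- If no report comes: followed literally, the dial stays at 4 or 5. Any patient whose threshold lies at or below that position is then left above the intended sub-threshold level. The dial positions are not translated into mA.

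**2. Share of planned stimulation (10.10, typical durations).**
Session 1 is 120 min and session 2 is 60 min, so the share is 120 / (120 + 60) = 0.667, or 67%.

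**3. Which sessions fall in the primary window?**
Protocol 2.3.1 counts 24 hours from the start of thrombectomy. For a start at clock time t, the window ends at t the next day. Session 2 is assumed to fall on the next calendar day (the synopsis speaks of two calendar days) and within 0800-1200h. It lasts 60 ± 10 min (6.7).
- Earliest possible end: 08:00 + 50 min = 08:50, or 08:00 + 60 min = 09:00.
- Session 2 can therefore be complete inside the window only for t at or after about 08:50-09:00. A session ending at 12:00 needs t at or after 12:00.
- For earlier starts, session 1 is the only complete session in the primary window.

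**4. Duration.**

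| Source | Session 1 | Session 2 |
|---|---|---|
| 6.7 and 10.10 | whole procedure, typically 120 min | 60 min |
| 9.2 | 30 min | 30 min |

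If the 30 minutes is a device timer (an assumption), session 1 delivers 30 / 120 = 25% of the plan, and both sessions together deliver (30 + 30) / 180 = 33%.

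**5. Would the data show it?**
Where the recorded end time is the operator's switch-off, an automatic stop would not change it. The stop would appear only if staff noticed it or the device log was read. Section 6.9 says the log holds periods of activation, and 10.5 says it holds delivery of programmed current. Neither 6.6 nor the SAP lists the log for collection, and 10.9 does not mention downloading it before disposal.

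No loss of power is calculated. The documents give neither the share of patients affected nor the direction: an unreduced dial gives more current than intended, and an early stop gives less stimulation.

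**The case against.** The strongest reply is that the plan is less open than it looks. Section 10.8 does give a starting position, so two operators who follow it to the letter in a silent patient differ by at most one division. Only staff trained by the manufacturer use the device, and each unit is tested and calibrated (10.1, 10.7, 10.8). The Instructions for Use, in Investigator Brochure appendix B, are the natural place for a rule on unresponsive patients and are not available here. The device logs programmed current, and the front label in 10.3 appears to carry a maximum-setting field. The trial is a phase IIa pilot.

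Much of this stands. A reader might infer that there is no amplitude rule at all. The documents do not support that: there is a rule and a literal starting position, but its sub-threshold step fails in patients who cannot report. A reader might also turn the usual 1-4 mA into a range of doses caused by this gap. Successful titration could produce the same spread. Nor should that range be widened by supposing that a timer acts in some patients only, since nothing suggests that devices of one type differ. Nor do the documents establish that the device stops at 30 minutes. Section 9.1 and the operator switch-off in 6.7 point the other way.

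The reply does not remove the conflict between 9.2 and 6.7/10.10, or the missing default. Training and calibration do not supply a setting that is nowhere stated. The label field has no stated purpose or route into the dataset. The deviation rule in 10.11 addresses a patient who stops or removes the device, not an automatic stop.

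**Conclusion.** The point holds and should be fixed. In patients who cannot report sensation, 10.8 cannot deliver the sub-threshold amplitude it intends in session 1. That session is about 67% of planned stimulation and, for thrombectomies starting before about 08:50-09:00, the only complete session in the primary window. The duration in 9.2 contradicts 6.7 and 10.10. If it is the timer, session 1 is cut to about 25% of plan.

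These sizes rest on the typical durations in 10.10, on session 2 falling the next calendar day, and, for the 25%, on the timer assumption. The Instructions for Use may contain a rule. If so, it belongs in 10.8, which as written directs something else.

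A reader might infer that the randomised comparison is biased. It is not on this account: intention-to-treat still compares sham with active treatment as delivered. What is unclear is the dose that was delivered.

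**What to change.** 1. **Section 10.8.** Titrate where the patient can respond and doing so does not delay thrombectomy. Otherwise use a stated default dial setting, with its mA equivalent from the manufacturer's calibration, inside the usual 1-4 mA. Write the steps so that the operator makes the same dial action in both arms. One fixed current for every patient is not recommended: it could exceed sensory threshold in sedated patients, who would then feel something that a switched-off sham never produces.
2. **Section 9.2.** Replace the 30 minutes with the durations in 6.7, and have the manufacturer confirm that the timer allows them.
3. **Recording.** Enter the dial setting per ear and session, kept from blinded assessors until database lock because a titrated setting can hint at allocation. Have the manufacturer confirm what the log stores, and add its download to 10.9 before disposal. Add a descriptive active-arm row to SAP Table 3: setting and minutes delivered, with no test.

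The cost is a few sentences, four fields per patient (2 ears x 2 sessions), one table row and one manufacturer check. No patients or visits are added. If sessions have already been delivered, the log download and the table row may still be possible.
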